12.0 Data Safety Monitoring Board

The Indiana University Adult Psychiatry Data Safety Monitoring Board (DSMB) will be responsible for data and safety monitoring. The DSMB is responsible for reviewing study procedures, adverse events, safety mailings (if applicable), enrollment, active subjects, and ongoing conduct of the research. The DSMB members can ask questions and make comments and/or recommendations. The IRB is notified of significant findings by way of the DSMB meeting

minutes at the time of continuing review. Due to the small sample size and single site design of this protocol, there is not sufficient justification for conducting interim analyses to examine trends. Data on the number of subjects enrolled and the number of adverse events will be reviewed by the DSMB every six months and more frequently if needed. The resultant report will be issued to the Indiana University IRB at least at the time of continuing review or more frequently by request. Any unanticipated events will be immediately directed to the PI who will follow the Indiana University IRB reporting procedures.

13.0 Statistical Considerations

Analyses

Power Analyses

In terms of the power to detect a significant effect of HF rTMS on CC neurocircuitry or performance, there are no known calculations with EPP patients. However, previous investigations, including our own, used similar stimulation designs when investigating the effects of rTMS on overall cognitive performance. These studies demonstrated statistically significant results with sample sizes consistent with the current proposal³², and Cohen's effect sizes of d = 0.92 and 1.15, respectively^{30,32}. Though these previous studies examined different cognitive constructs than the CC task in this current protocol, these studies do provide evidence that a similar stimulation design is sufficient to elicit a biologic response and assumedly appropriate for investigating the effects of rTMS on CC.

We believe that for the purpose of this pilot study, we can demonstrate significant results with a sample size of 16 (eight per group). This accounts for the effect size estimate derived from the literature, d = 1.1, and the estimation of power to detect an effect at .75, utilizing a one-sided independent test and significance levels of 0.05.

Statistical Analyses

Preliminary analyses will consist of descriptive statistics for all outcome variables, including summary statistics, graphical displays of distributions, and spaghetti plots of individual data over time to detect possible data errors. Demographic and clinical characteristics at baseline will be examined using parametric or nonparametric test statistics as appropriate. Any demographic variables that show significant differences will be added to the final models as covariates in order to ensure that the observed stimulation effects are not spurious or due to demographic confounds.

To minimize the potential for Type II error, all treatment comparisons will be evaluated based on a one-sided significance level of 0.05. To compare overall effect of stimulation over time for the two groups, a set of multivariate repeat measures analysis of variance (ANOVA) will be utilized, with stimulation as the between-group factor and time as the within-subject factor.

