3.0 Study Design

This will be a single site pilot study. 20 subjects with EPP, defined as medical record documentation of the onset of clinically significant psychotic symptoms within the past 10 years, will be enrolled. Prior to randomization subjects will undergo fMRI during CC task (Stroop Color-Word paradigm) and resting-state paradigms. This baseline scan will also

include a high-resolution structural sequence for neuronavigation purposes. Then, on two separate days, each occurring one-week apart, subjects will receive one session of excitatory (20 Hz) rTMS targeting the LDLPFC and one session targeting the LSPC. The order of stimulation sites will be randomized and counter-balanced. Immediately following each session, subjects will undergo repeat fMRI during CC and RS paradigms. We will also examine the effect of rTMS on CC performance.

rTMS Set up and Administration

rTMS will be delivered using the Magventure MagPro X100 Magnetic Stimulator (Magventure Inc., Alpharetta, Georgia). Motor threshold (MT) will be determined using single pulse stimulation over the left primary motor cortex, assessed as the lowest intensity producing five visible movements of the right abductor pollicis brevis out of ten stimulations.

High Frequency rTMS

High frequency rTMS, or rTMS greater than 5 Hz, leads to faciliatory effects on brain excitability^{20-24,31}. Previous studies have demonstrated that administration of as little as a single train or a small number of trains are able to produce an immediate increase in cortical excitability²⁴. Additionally, earlier investigations have utilized high frequency rTMS in schizophrenia populations, demonstrating that the treatment is safe, well-tolerated and capable of altering cognitive performance^{30,32}. Our group has employed 20 Hz rTMS at 110% of motor threshold in a stimulation protocol in-line with the current proposal to improve cognitive function in an EPP cohort³⁰. High Frequency rTMS Protocol: Subjects will receive two sessions of HF rTMS, targeting the LDLPFC and LSPC, within the following stimulation parameters: 20 Hz, at 120% of MT, 60 trains (1.0 second per train), 20 pulses per train, inter-train interval of 20 seconds, for a total of 1200 pulses over 21 minutes. This stimulation protocol is within safety limits for rTMS^{21,33,34}.

Neuronavigation

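### Section 13 sizes and analyses a two-group comparison that the trial does not have, and its stated power of .75 is about 0.67 on its own inputs

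*Combined protocol and SAP*

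**What the plan says.** **Section 13.0, Power Analyses.** The sponsor expects to "demonstrate significant results with a sample size of 16 (eight per group"). The basis is a literature effect of d = 1.1 and "the estimation of power to detect an effect at .75, utilizing a one-sided independent test and significance levels of 0.05". The two source studies are reported with "effect sizes of d = 0.92 and 1.15".

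**Section 13.0, Statistical Analyses.** The model is a multivariate repeated-measures ANOVA. Its purpose is given as "To compare overall effect of stimulation over time for the two groups", "with stimulation as the between-group factor and time as the within-subject factor". In addition, "all treatment comparisons will be evaluated based on a one-sided significance level of 0.05".

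**Section 3.0, Study Design.** After a baseline fMRI, "subjects will receive one session of excitatory (20 Hz) rTMS targeting the LDLPFC and one session targeting the LSPC", one week apart, with fMRI repeated after each session. "The order of stimulation sites will be randomized and counter-balanced". The Study Procedures Table (Attachment 1) likewise lists randomization as concerning the order of the intervention. No sham or untreated arm is described.

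**Section 3.0, Sample Size.** The same 16 completers (20 enrolled, 20% dropout) are said to give 0.8 power for an effect size of 0.6, with alpha 0.05 and within-subject correlation 0.5.

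**Section 2.0.** Both primary aims predict an increase after rTMS: in ACC activation (aim 1) and in connectivity among the LDLPFC, LSPC and ACC (aim 2). The text predicts no difference between the two sites.

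**The concern.** Section 13 and Section 3 describe different trials. When every subject receives both active sessions, stimulation varies within subjects. The only groups that last through the study are the two site orders. With no control arm, an increase after rTMS can be measured only against each subject's own baseline scan, and Section 13 neither names that contrast nor bases its power on it.

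The two-group comparison does not answer either primary aim. The analyst is also left to choose the primary contrast once the data are in, and the candidates differ appreciably in power. Separately, the .75 does not follow from the inputs printed beside it, and it sits next to a second, incompatible justification for the same 16 completers.

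**Working it through.** **1. The stated .75.** Inputs from Section 13: 8 per group, d = 1.1, one-sided alpha 0.05, independent test.

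- Noncentrality = d × √(n/2) = 1.1 × √(8/2) = 2.2, with 14 degrees of freedom.
- t-test (noncentral t): power 0.673.
- Normal approximation: Φ(2.2 − 1.645) = 0.711.

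Neither gives .75. The two source effect sizes do not either:

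| d | t-test | normal approximation |
|---|---|---|
| 0.92 | 0.542 | 0.577 |
| 1.10 | 0.673 | 0.711 |
| 1.15 | 0.706 | 0.744 |

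With 8 per group, .75 requires d = 1.22 (t-test) or 1.16 (normal). At d = 1.1 it requires 10 per group (t-test, 0.764) or 9 per group (normal, 0.754).

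**2. What a two-group comparison can detect here.** Assume unit SD, correlation 0.5 (Section 3) and 8 subjects per order.

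- *Both sites add 0.6 SD to baseline* (equal effects are an assumption, consistent with Section 2). The two order groups then have the same expected values at every scan. In 100,000 simulated trials at one-sided 0.05, rejection was 0.0496 for the order-group main effect and 0.0507 for site by time up to the first post-stimulation scan. Both are just alpha.
- *One site adds 0.6 and the other 0.* For the change from baseline to the first post-stimulation scan, the SD is √(2 × (1 − 0.5)) = 1. Noncentrality = 0.6 × √(8/2) = 1.2 with 14 df, and power is 0.31.

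**3. The 0.8 in Section 3.** Section 3 names no test or contrast, so contrasts have to be assumed. Inputs: n = 16, effect 0.6, correlation 0.5, taken as equal between all pairs of scans.

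- *One site against baseline.* Standardized difference = 0.6/√(2 × (1 − 0.5)) = 0.6. Noncentrality = 0.6 × √16 = 2.40, df 15.
- *Mean of both post-stimulation scans against baseline.* Variance = (1 + 0.5)/2 + 1 − 2 × 0.5 = 0.75. Standardized difference = 0.6/√0.75 = 0.693. Noncentrality = 0.693 × √16 = 2.771, df 15.
- *Omnibus test of three conditions* with means 0, 0.6, 0.6. The sum of squares about the mean 0.4 is 0.16 + 0.04 + 0.04 = 0.24, so lambda = 16 × 0.24/(1 − 0.5) = 7.68.

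| Contrast | one-sided | two-sided |
|---|---|---|
| One site against baseline, paired t | 0.740 | 0.612 |
| – normal approximation | 0.775 | 0.670 |
| Mean of both against baseline, t | 0.841 | 0.736 |
| – normal approximation | 0.870 | 0.791 |

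The omnibus test has no direction. Its power is 0.652 in the univariate form, F(2,30), and 0.597 in the multivariate form, F(2,14). Adding an order term to the mean-of-both contrast (df 14) changes its one-sided power only to 0.839.

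The stated 0.8 lies inside this range, but without a named contrast it can be neither confirmed nor refuted.

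**The case against.** The strongest reply is that the planned ANOVA contains time as a within-subject factor. Because everyone is stimulated after baseline, the time effect captures the change that the aims need, so only one factor is mislabelled. That is true of the model. However, Section 13 states its purpose as comparing two groups, sizes the trial on an independent test and never names the time effect as the primary test. The 5% rejection rate applies to the between-group and interaction terms, not to the time term.

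A second reply is that sidedness is not really open, because Section 13 sets one-sided 0.05 for all treatment comparisons. Held to that rule, the two change-from-baseline contrasts give 0.74 to 0.84 by t-test, on either side of Section 3's 0.8. This is fair, and it is why the 0.8 is not called wrong. The test and contrast remain unnamed all the same, and the low value of 0.60 belongs to the multivariate ANOVA that Section 13 itself specifies.

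Third, the power error is modest: at d = 1.1 the shortfall is one subject per group by normal approximation or two by t-test, and d = 1.15 with the normal approximation gives 0.744. This stands. Alone it would be a minor correction.

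Finally, a figure captioned as the aim 2 prediction is not visible in the text reviewed, so the statement that no site difference is predicted covers the text only. Pooling both sites is also one choice among several, and it would not show that either site works alone.

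**Conclusion.** The concern holds and must be fixed, mainly because the analysis and power basis in Section 13 contradict the design in Section 3. The comparison that is powered and described tests orders or sites, not rTMS against baseline. Its power is 0.05 if both sites work equally and about 0.31 if only one adds 0.6 SD.

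On its own inputs the .75 should be 0.67 (t-test) or 0.71 (normal approximation). This part needs no outside assumption.

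The within-subject figures, about 0.60 to 0.84 depending on contrast and sidedness, rest on Section 3's effect size and correlation plus assumed equal site effects, where both sites enter the contrast, and equal correlations between scans. They show that the contrast must be named. They do not show that 16 completers are too few.

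**What to change.** 1. Delete the eight-per-group power paragraph from Section 13. If it is kept, restate the power as about 0.67 (independent t-test) and say that this is not the design of the trial.
2. Replace the ANOVA description with one that fits Section 3, for example: stimulation condition (baseline, after LDLPFC, after LSPC) is the within-subject factor and stimulation order is the between-subject factor.
3. Name the primary within-subject contrast for the two aims and its sidedness, such as the mean of both post-stimulation scans against baseline, or each site against baseline.
4. Give one power statement in both Sections 3 and 13, computed for that contrast and not for the omnibus test. With 16 completers, effect 0.6, correlation 0.5 and one-sided 0.05, it would be 0.84 for the mean of both scans or 0.74 for each site (t-tests, equal correlations, no multiplicity adjustment).

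The cost is wording in two sections. Enrolment and procedures do not change. The stated power may end up above or below 0.8, depending on the contrast chosen.

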Brainsight software (Rogue Research, Montreal Canada) will be used to reliably target the LDLPFC and LSPC for stimulation. First, the subject's individual anatomy will be registered stereotactically using the acquired structural MPRAGE brain image and fiduciary points on the scalp visible with a Polaris vicar camera (Brainsight software). We will use the centers of mass of the LDPLFC and LSPC (derived via Freesurfer parcellation; Destrieux Atlas³⁵; left/right combined) to identify the specific coordinates for stimulation. Stimulation sites will be marked on a swim cap worn by the subjects at each stimulation session, consistent with prior TMS studies²⁵.

Electrical field modeling

The processed structural image will be used to generate E-fields based on realistic conductor head models using SimNIBS (2.1 or latest version). SimNIBS includes volume conductor

modeling (following FreeSurfer segmentation), TMS coil specific magnetic dipole estimations, and finite element modeling of the electric field at each tetrahedral element of the subject's head mesh. In anticipation of actual TMS sessions with each patient, we will find the optimal TMS positioning to most strongly influence the LDLPFC and LSPC, which will be the target for neuronavigated rTMS delivery.

rTMS administration monitoring

All subjects will be instructed to wear earplugs during each rTMS session and will be monitored by medically trained research staff throughout the entirety of each rTMS session.

Duration of Treatment

Subjects will complete two stimulation sessions over two weeks, with one session occurring each week. Previous work has demonstrated that a single session of rTMS is sufficient to modulate target site functional activation as well as functional connectivity between the stimulation target and associated circuitry²⁵.

Sample Size

We plan to enroll 20 subjects and anticipate a 20% drop out rate, yielding 16 completers. This is consistent with our previous clinical trial efforts, including a study of adjunct rTMS in an EPP cohort^{30,36}. For all planned analyses, a total of 16 subjects in a counter-balanced design will result in 0.8 power to detect an assumed stimulation effect at medium effect size 0.6; using an alpha level of 0.05 and conservatively assumed a within-subject correlation of 0.5. As no CCN rTMS pilot data was available, this standardized effect size of 0.6 is considered a conservative estimate to detect significant results.

Clinical Research Site

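### The power of .75 in Section 13.0 does not follow from its own inputs: eight per group, d = 1.1 and a one-sided independent test at 0.05 give 0.67 by exact t (0.71 by normal approximation)

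*Combined protocol and SAP*

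**What the plan says.** Section 13.0, Power Analyses, states that "we can demonstrate significant results with a sample size of 16 (eight per group"). It bases this on "the effect size estimate derived from the literature, d = 1.1", on "the estimation of power to detect an effect at .75", and on "utilizing a one-sided independent test and significance levels of 0.05". The paragraph before it reports the two earlier studies behind the effect size, with "Cohen's effect sizes of d = 0.92 and 1.15, respectively". The Statistical Analyses text in the same section repeats the sidedness: "all treatment comparisons will be evaluated based on a one-sided significance level of 0.05".

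Section 3.0, Sample Size, shows where the 16 comes from. The plan is to enrol 20 and "anticipate a 20% drop out rate, yielding 16 completers". That section also makes a separate power statement for the same 16 subjects: 0.8 at an effect size of 0.6, in a counter-balanced design with a within-subject correlation of 0.5.

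**The concern.** The Section 13.0 sentence gives everything a two-group power calculation needs: group size, standardised effect, type of test, sidedness and alpha. It should therefore reproduce, and it does not. The standard calculations on those inputs all fall below .75.

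The sentence is Section 13.0's reason for believing that 16 subjects are enough. Anyone relying on it gets a more favourable picture than its inputs allow. There is also a practical risk: if the section is later revised to fit the design, a figure that was never right on its own terms could be carried into the new text.

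**Working it through.** **Inputs**, all from Section 13.0: n = 8 per group, d = 1.1 (standardised, so SD = 1), independent groups, one-sided alpha = 0.05. Stated power: 0.75.

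**Exact two-sample t**
- Degrees of freedom: 8 + 8 − 2 = 14.
- Noncentrality: d × √(n/2) = 1.1 × √(8/2) = 2.2.
- One-sided 5% critical value of t on 14 df: 1.761.
- Power = P(noncentral t on 14 df with noncentrality 2.2 exceeds 1.761) = 0.673. A simulation of 400,000 trials gives 0.672.
- Gap: 0.75 − 0.673 = 0.077, about 8 points.

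**Normal approximation**
- Power = Φ(2.2 − 1.645) = Φ(0.555) = 0.711.
- Gap: 0.75 − 0.711 = 0.039, about 4 points.

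**Other readings of the same inputs**
- Two-sided exact t: 0.535. Two-sided normal approximation: 0.595.
- Rank test, by adjusting the exact t for its relative efficiency: 0.61 to 0.65.

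None of these comes within two points of .75, and all are below it.

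**Effect needed for .75 with eight per group**
- Exact t: d = 1.22.
- Normal approximation: (1.645 + 0.674) / 2 = 1.16.

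Both exceed the larger cited effect of 1.15.

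**Power at the two cited effects** (eight per group, one-sided exact t)
- d = 0.92: 0.542.
- d = 1.15: 0.706.

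**What has to change to get near .75**
- d = 1.1, 9 per group, normal approximation: Φ(1.1 × √4.5 − 1.645) = 0.754. Exact t at 9 per group: 0.722.
- d = 1.1, 10 per group, exact t: 0.764.
- d = 1.15, 9 per group, exact t: 0.755.
- d = 1.15, 8 per group, normal approximation: 0.744.

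Each of these changes the group size or the effect size from what the sentence states. Several changes give roughly the same answer, so the arithmetic does not show how .75 arose.

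**The case against.** The strongest objection is that the calculation describes a comparison this trial does not make. Under Section 3.0 every subject has a baseline scan and then receives both stimulation sites, and Attachment 1 shows that only their order is randomised. An eight-versus-eight independent test is not the contrast this design yields, so putting 0.67 in place of .75 would give a corrected figure for the wrong test and leave the conflict with Section 3.0's power statement untouched. This stands. It limits what the correction achieves and shapes the fix. It does not make .75 right for the basis on which the plan states it.

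A second objection is that the plan names neither a t-test nor a power method, so a gap of 8 points should not be stated as if it were the only answer. This also stands. The normal approximation halves the gap, so the range of 4 to 8 points is the fair statement. Exact t is the better choice at 14 degrees of freedom, and both methods show the stated power as too high.

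A third objection is that this is a single-site pilot and the correction changes no endpoint, analysis or sample size. That is fair, and it keeps the point modest.

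Three stronger readings are tempting, and the documents do not support them:
- A reader might infer that .75 was computed on the 20 enrolled (10 per group) and not on the 16 completers. That is possible but unproven, since 9 per group or d = 1.15 comes equally close.
- A reader might infer that the trial's chance of missing its planned effect is 33% (1 − 0.67) and not 25% (1 − 0.75). Both figures belong to the independent-groups test, so neither is a property of a design in which each subject receives both sites.
- A reader might object to d = 1.1 because it lies near the larger cited effect. It is inside the cited range of 0.92 to 1.15, and choosing it is not an arithmetic error.

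**Conclusion.** The point holds as an error of arithmetic within Section 13.0. On the inputs stated there, power is 0.67 by exact t and 0.71 by normal approximation, against a stated .75. The figure is too high by about 4 to 8 points, and at eight per group it cannot be reached by either method with either cited effect.

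The result assumes a parametric comparison of two equal groups with d standardised by a common SD. It needs no input from outside the document. It gives neither the power of the within-subject design nor a judgement on the power statement in Section 3.0, which rests on a different basis.

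**What to change.** Which edit applies depends on what happens to the paragraph.

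- **If the independent-groups calculation is kept:** in Section 13.0, replace .75 with 0.67 and state the method and sample (exact two-sample t, 16 completers). Optionally add that power runs from 0.54 to 0.71 over the two cited effects.
- **If Section 13.0 is rewritten for the within-subject design in Section 3.0 and reconciled with the power statement there:** delete the .75 and do not carry it over. This is the more useful course, because correcting the number alone does not remove the mismatch with the design.

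The first edit takes one sentence. The second adds no work to a rewrite that is being done anyway. Neither requires more patients or changes a study procedure. The only downside is that, if the calculation is kept, the stated power is less favourable.

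### Choosing covariates by baseline significance tests gives no protection against confounding when every subject receives both sites, and it lets chance decide the final model

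*Combined protocol and SAP*

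**What the plan says.** Section 13.0 (Statistical Analyses) begins with baseline testing: "Demographic and clinical characteristics at baseline will be examined using parametric or nonparametric test statistics as appropriate". It continues: "Any demographic variables that show significant differences will be added to the final models as covariates", and gives the reason as "in order to ensure that the observed stimulation effects are not spurious or due to demographic confounds". It does not list the candidate variables, set a threshold for these tests, say which groups are compared, or say how a covariate enters the model (centred or not, with or without a time interaction).

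The model in the same section is a repeated measures ANOVA "with stimulation as the between-group factor and time as the within-subject factor", and "all treatment comparisons will be evaluated based on a one-sided significance level of 0.05". The power paragraph there counts 16 subjects as eight per group.

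Section 3.0 describes a different structure: "subjects will receive one session of excitatory (20 Hz) rTMS targeting the LDLPFC and one session targeting the LSPC", and "The order of stimulation sites will be randomized and counter-balanced". The Study Procedures Table (Attachment 1) also shows order as the thing randomised.

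**The concern.** The rule is borrowed from a parallel-group trial. Here each subject is their own control for site, so age, sex or education cannot differ between sites. Compared by site, the rule never fires. It can fire only if the two order groups are compared, and those groups are formed by randomisation, so a significant difference between them is chance.

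At stake is whether the model behind each aim is fixed in advance. With about 16 completers, one extra covariate can change a p-value noticeably, and under this rule a chance result decides whether it enters. Section 13.0 justifies one-sided testing by a wish to limit Type II error; a rule that can cost power works against that.

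**Working it through.** **Inputs from the documents.** Section 3.0 (Sample Size): 16 completers, effect 0.6, within-subject correlation 0.5. Section 13.0: eight per group, one-sided 0.05.

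**Assumed, because the plan is silent.** The number k of demographics tested, selection at two-sided 0.05 between order groups, and each covariate's mean/SD ratio.

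**Plan's own figures.** None is given for the covariate rule. The reference power comes from the Section 3.0 inputs. The standardised paired difference is 0.6/√(2(1 − 0.5)) = 0.6, and the noncentrality is 0.6 × √16 = 2.4. A one-sided paired t-test then has power 0.74 (0.77 by the normal approximation), against the stated 0.8. That gap is a separate matter and nothing below depends on it.

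**1. How often the rule fires.** For independent continuous variables the probability of adding at least one is 1 − 0.95^k:
- k = 4: 1 − 0.8145 = 19%
- k = 8: 1 − 0.6634 = 34%

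A binary variable under Fisher's exact test at 8 v 8 is flagged only 0.4% to 2.1% of the time (prevalence 0.2 to 0.5), so a list with many categorical variables gives lower figures.

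**2. Site contrast.** With site order counterbalanced, the site effect is the order-by-period term: the difference between order groups in the change from first to second session.
- Selection at 8 v 8 needs t of at least 2.145 on 14 df, a difference of 2.145 × √(2/8) = 1.07 SD.
- Order then explains at least 2.145²/(2.145² + 14) = 4.60/18.60 = 0.247 of the covariate's variance.
- If the covariate may interact with time, the standard error of the site contrast is inflated by at least 1/√(1 − 0.247) = 1.15. The noncentrality falls from 2.4 to at most 2.08, on 13 df.
- Simulation with outcome-unrelated covariates and k = 5, among trials in which at least one was selected: power about 0.73 to 0.75 without the covariate and 0.58 with it. Centring makes no difference, because the loss comes from correlation with order.
- Averaged over all trials: 0.19 × (0.73 − 0.58) ≈ 0.03 to 0.34 × 0.15 ≈ 0.05, or 3 to 5 points. This holds 0.58 fixed across k.

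**3. Pre-post time test.** If a covariate enters with a time interaction and uncentred, the time term is the change at covariate value zero. For one covariate with mean/SD ratio r, its standard error is inflated by about √(1 + r² × 16/14):

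| r | Inflation | Power |
|---|---|---|
| 1 | 1.46 | 0.46 |
| 2 | 2.36 | 0.24 |
| 3 | 3.36 | 0.16 |
| 4.5 (e.g. age 27, SD 6, assumed) | 4.91 | 0.12 |
| 6 | 6.49 | 0.10 |

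With the covariate centred, power is 0.74, the same as with none. With an uncentred main effect only, checked in a mixed model on one simulated dataset, the time estimate and its standard error did not change (0.566, SE 0.297). Adding the interaction gave 2.446, SE 1.671.

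**4. Type I error.** With no true effect, rejection stayed at 0.05 to 0.06 for the time test in every version. For the site contrast it was 0.051 without and 0.046 with the selected covariate.

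**The case against.** The best defence is that the loss depends on choices Section 13.0 does not make. It says only that covariates are added. An analyst who adds a subject-level main effect to a within-subject model leaves both the site contrast and the time test essentially untouched. This is also a 20-subject pilot, and the more basic fault is a between-group model for a design in which everyone receives both sites.

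Much of that stands, and it rules out three stronger readings.

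- A reader might infer that the plan's own text drops time-test power from 0.74 to 0.10. That needs an uncentred covariate, a time interaction and a high mean/SD ratio together; the plan states none of them. The section's wording is also not clearly about the time main effect, although the first aim does imply a pre-post comparison.
- A reader might infer more false positives. The simulations show none.
- A reader might fault the test for missing real imbalances at 8 v 8. With order randomised there is no true difference to find.

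One caution runs the other way. A chance imbalance in something that modifies session or practice effects could distort the site contrast in a given sample. Testing baseline for significance is still not the remedy; prespecifying the covariate is.

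The defence does not rescue the rule. Under either choice of groups it cannot deliver the protection claimed. Correcting the ANOVA alone would leave the sentence in force.

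**Conclusion.** The point holds in a limited form. The rule either never operates (sites compared) or selects on chance (orders compared), so it gives no protection against demographic confounding of the stimulation effect and leaves the final model undetermined until baseline p-values are seen.

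The cost is moderate lost power, not false positives. If a selected covariate may interact with time, the site contrast falls from about 0.73 to 0.58 in the trials affected. The 3-to-5-point average assumes 4 to 8 independent continuous variables and would be smaller with categorical ones. Larger losses in the time test are possible only if the covariate is also uncentred, and they vary widely with its scale.

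**What to change.** In Section 13.0, replace the significance-based sentence with a fixed specification:

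- Describe baseline characteristics by randomised order, without tests.
- Fit a within-subject model containing site (or scan, where baseline is included), session and randomised order.
- If age, sex or another covariate is wanted, name it before data are analysed, enter it mean-centred, state whether it interacts with time, and keep it whatever its baseline p-value.

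This costs a few sentences in one section. It adds no data, visits or procedures. The covariate sentence needs its own edit even if the between-group ANOVA is corrected separately.
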